10.1.1.3. Secondary Endpoint: Blood loss

Missing blood loss values for some eschar removal procedures may occur within a certain patient. A regression model containing main prognostic factors (wound area, depth of wound and type of procedure) for blood loss of eschar removal procedures will be computed on a procedure level treating all procedures as independent. On this basis a multiple imputation will be calculated. The procedure can be described as follows:

1. Test for normality: The Shapiro-Wilk test will be performed on the dataset of non-missing values in each treatment group. The result of these tests will determine the type of the analysis on the imputed data sets (step 3). If the normal distribution hypothesis is not rejected at the 5% significance level in either group, then differences in distribution between NexoBrid and SOC will be tested using a t-test. If the normal distribution hypothesis is rejected either in the NexoBrid group or in the SOC group, then the differences in distribution between the treatment groups will be tested using a Mann-Whitney test.
2. Imputation: Fit a linear regression model with target variable blood loss on a procedure level (as computed in Section 10.3.3.3) and dependent variables size of wounds treated in this procedure (wound area), proportion of area SPT of wounds treated in this procedure (as defined in Section 10.3.3.3.2), proportion of area DPT of wounds treated in this procedure (as defined in Section 10.3.3.3.3), proportion of area FT of wounds treated in this procedure (as defined in Section 10.3.3.3.4) and type of

procedure (surgical/non-surgical) to the subset containing patients with complete data in those variables for both treatment groups separately. Impute the missing entries of the incomplete data sets $m = 25$ times as follows: Draw a set of regression coefficient from their sampling distribution obtained from fitting the respective linear models outlined above (a different distribution for the regression coefficients will be obtained in the different treatment groups). With these sampled coefficients calculate the predicted blood loss values for the procedures with missing blood loss using the covariate information. To these predicted blood loss values add the realizations of a normally distributed random variable with zero mean and standard deviation equal to the residual standard deviation from the linear model fitted to the complete data set. The random seeds for these 25 imputations will be (11468, 11469, 11470, ..., 11492). On the imputed datasets calculate the blood loss on a patient level.

3. Analysis: Analyze each of the m complete data sets with a t-test or the Mann-Whitney test according to the test result in step 1. This step results in m estimates of the effect and m estimates of the standard deviation.
4. Pooling: Integrate the m analysis results into a final result with the SAS procedure PROC MIANALYZE according to Rubin's combination rules for multiple imputation to obtain the final estimates of mean and variance [28].

For the additional analysis of blood loss which treats the whole eschar removal process as one continuous procedure (see section 7.3.2.2) the multiple imputation will be performed on a patient level. The procedure can be described as follows:

1. Test for normality: The Shapiro-Wilk test will be performed on the dataset of non-missing values in each treatment group. The result of these tests will determine the type of the analysis on the imputed data sets (step 3.). If the normal distribution hypothesis is not rejected at the 5% significance level in either group, then differences in distribution between NexoBrid and SOC will be tested using a t-test. If the normal distribution hypothesis is rejected either in the NexoBrid group or in the SOC group, then the differences in distribution between the treatment groups will be tested using a Mann-Whitney test.
2. Imputation: Fit a linear regression model with target variable blood loss on a patient level (as computed in Section 10.3.3.3) and dependent variables wound area, depth of wound (categorized as described in Section 11.1.10) and course of debridement procedure (as defined in Section 10.3.3.3.5) to the subset containing patients with complete data in those variables for both treatment groups separately. Impute the missing entries of the incomplete data sets $m = 25$ times as follows: Draw a set of

regression coefficient from their sampling distribution obtained from fitting the respective linear models outlined above (a different distribution for the regression coefficients will be obtained in the different treatment groups). With these sampled coefficients calculate the predicted blood loss values for the procedures with missing blood loss using the covariate information. To this predicted blood loss values add the realization of a normally distributed random variable with zero mean and standard deviation equal to the residual standard deviation from the linear model fitted to the complete data set. The random seeds for these 25 imputations will be (12467, 12468, 12469, ..., 12491). On the imputed datasets calculate the blood loss on a patient level.

3. Analysis: Analyze each of the m complete data sets with a t-test or the Mann-Whitney test according to the test result in step 1. This step results in m estimates of the effect and m estimates of the standard deviation.
4. Pooling: Integrate the m analysis results into a final result with the SAS procedure PROC MIANALYZE according to Rubin's combination rules for multiple imputation to obtain the final estimates of mean and variance [28].

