10.3.3.3. Secondary Endpoint: Blood loss

10.3.3.3.1. Blood loss for main analysis

For each patient and each procedure carried out to remove eschar the estimated blood volume (EBV) will be calculated as

$$EBV = 70 \frac{cm^3}{kg} * weight(kg)$$

Furthermore, the total volume of whole blood and packed red blood cells (PRBC) transfused (in milliliters) will be calculated per procedure (transfusions given during the procedure and 4 hours \pm 15 minutes later) and denoted by V_{WB} and V_{PC} in the following.

From these quantities, the blood loss (Actual Blood Loss, ABL) will be calculated using the following formula [25]:

$$ABL = \frac{EBV * (Hb_{before} - Hb_{after})}{(Hb_{before} + Hb_{after})/2} + V_{WB} + \frac{5}{3}V_{PC}$$

The factor of 5/3 is derived from chapter 5 of Transfusion Medicine, 4th Edition [31] and compensates for the fact that equal volumes of whole blood and packed red blood cells are not comparable.

The ABL will be summed over all procedures carried out to remove eschar, with the Hb measured immediately before each procedure and 4 hours after its completion. The amount of blood transfused will be summed over all transfusions carried out during the debridement procedure and 4 hrs later i.e. the before-after periods that are spanned by these Hb measurements.

Additionally, blood loss will be computed considering the whole debridement process as one continuous procedure. For this value, the formula for ABL given above will also be used. However, the ABL will be computed using the Hb measured immediately before the first procedure and 4 hours after completion of the last procedures. The amount of whole blood and packed red blood cells (PRBC) transfused will be calculated as before, but incorporating all such transfusions in the time frame spanned by the Hb measurements used for the calculation (pre first procedure to 4 hrs post last procedure (in which complete debridement was achieved).

Analyses with both blood loss values will be conducted. However, some missing values are expected. The analysis with less missing values will be regarded as more reliable and is therefore considered the main analysis. The other analysis is considered supportive.

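### The procedure-wise blood-loss imputation ignores clustering within patients; if residual blood loss is positively correlated within patients, the pooled standard error in the t-test branch is modestly too small

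*SAP*

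**What the plan says.** SAP section 10.1.1.3 describes two imputations. For the procedure-wise measure, a linear model for blood loss is "computed on a procedure level treating all procedures as independent". It is fitted separately in each arm. Its predictors are wound area, the SPT, DPT and FT proportions, and whether the procedure was surgical. There is no patient term, and neither body weight nor the patient's other procedures are used.

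The draw has two parts. The plan says "Draw a set of regression coefficient from their sampling distribution obtained from fitting the respective linear models outlined above", and then adds normal noise with "standard deviation equal to the residual standard deviation from the linear model fitted to the complete data set". This is done 25 times.

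Next comes aggregation: "On the imputed datasets calculate the blood loss on a patient level". Section 10.3.3.3.1 defines that total: "The ABL will be summed over all procedures carried out to remove eschar". Each completed data set goes to a t-test or a Mann-Whitney test, depending on Shapiro-Wilk, and results are combined "according to Rubin's combination rules for multiple imputation to obtain the final estimates of mean and variance".

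The second measure treats the whole eschar-removal period as one procedure and is imputed at patient level. Sections 7.3.2.2, 10.3.3.3.1 and 11.1.3.3 make whichever measure has fewer missing values the main analysis. Blood loss is fourth and last in the hierarchy of section 11.1.8.

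**The concern.** The analysed quantity is a sum within a patient, so its variance contains the covariances between that patient's procedures. Imputing one procedure without reference to the others sets those residual covariances to zero wherever a value is missing. The coefficient draws also count clustered rows as independent. With positive correlation both effects shrink the variance that Rubin's rules report.

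The SAP itself gives a reason to expect positive correlation. Every procedure value is scaled by an estimated blood volume of 70 cm³ per kg, and weight is common to all procedures of a patient but absent from the imputation model.

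The plan allows for clustering elsewhere: patient random effects in the wound-level logistic models (11.1.2, 11.1.3.1), and a robust variance or shared frailty for wound closure (11.1.4.1). What is at stake is the width of the interval for blood loss and, if this measure becomes the main one, the level of the last test in the hierarchy.

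**Working it through.** **Inputs from the SAP.** 75 patients each in the NexoBrid and SOC arms (9.3.1); 25 imputations (the listed seeds 11468 to 11492 are indeed 25); two-sided 5% level (11.1.8). Blood loss has no sample-size calculation, and no SD, correlation or missing rate is stated for it, so there is no plan figure to reproduce.

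**Assumptions.** k procedures per patient, residual variance σ², common within-patient correlation ρ, a fraction p of procedure values missing completely at random, no true difference, normal errors.

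**Approximation.** Leave covariates aside, drop the 1/25 correction, and work per arm in units of kσ²/n.

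- Within-imputation variance. A pair of procedures keeps its covariance only if both are observed, with probability (1−p)²: W = 1 + (k−1)ρ(1−p)².
- Between-imputation variance. Noise contributes p, and the coefficient draw, counting nk(1−p) independent rows, contributes p²/(1−p). Together B = p/(1−p).
- Reported variance: T = W + B = 1/(1−p) + (k−1)ρ(1−p)².
- True variance. The pooled mean total is close to k times the mean of the observed procedures, so V = 1/(1−p) + (k−1)ρ.
- Ratio of reported to true SE: √(T/V). It is 1 when ρ = 0, below 1 when ρ > 0 and above 1 when ρ < 0.

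**Against simulation of the SAP's algorithm** (75 v 75, two covariates, t-test branch, 800–3,000 replicates, Monte Carlo error about 1.3–2.5% on the ratio):

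| k | ρ | p | V | T | √(T/V) | Simulated ratio | Simulated type I error |
|---|---|---|---|---|---|---|---|
| 2 | 0 | 0.2 | 1.25 | 1.25 | 1.00 | 1.002 | 0.053 |
| 2 | 0.5 | 0.2 | 1.75 | 1.57 | 0.95 | 0.976 | 0.055 |
| 3 | 0.5 | 0.1 | 2.11 | 1.92 | 0.95 | 0.976 | 0.057 |
| 3 | 0.5 | 0.2 | 2.25 | 1.89 | 0.92 | 0.904 | 0.078 |
| 3 | 0.5 | 0.3 | 2.43 | 1.92 | 0.89 | 0.917 | 0.077 |
| 4 | 0.6 | 0.3 | 3.23 | 2.31 | 0.85 | 0.83 | 0.112 |
| 2 | −0.4 | 0.2 | 0.85 | 0.99 | 1.08 | 1.091 | 0.031 |
| 3 | −0.3 | 0.3 | 0.83 | 1.13 | 1.17 | 1.149 | 0.025 |

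**A mix of 1–3 procedures.** Replace k−1 by E[k(k−1)]/E[k]. With equal shares of 1, 2 and 3 procedures this is (0+2+6)/(1+2+3) = 1.33.

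- ρ = 0.3, p = 0.1: √(1.435/1.511) = 0.975, a shortfall of 2.5%.
- ρ = 0.6, p = 0.2: √(1.762/2.050) = 0.927, a shortfall of 7.3%.
- ρ = 0.6, p = 0.4: √(1.955/2.467) = 0.890, a shortfall of 11.0%.

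Variance explained by covariates enters both sides and dilutes these figures. Simulation at 1,000 replicates per setting (ρ 0.3–0.6, 1–3 procedures) gave about 0–5% at 10–20% missing and 4–9% at 40%, with type I error about 0.04–0.08. A 500-replicate run at ρ = 0.6 gave 9–11% at 20–40% missing. About 15% was reached only when every patient had three procedures and 40% of values were missing.

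**The fixed residual SD.** Redrawing it on the same simulated data sets moved the ratio by 0.001–0.004, for example from 0.904 to 0.906.

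**The remedy.** Random-intercept imputation with drawn variances (3 procedures, ρ 0.3–0.6) gave ratios of 0.95–1.05 and type I error of 0.048–0.061.

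**The case against.** **This measure will probably not be the main one.** The whole-period measure needs only the haemoglobin before the first procedure and after the last. The procedure-wise total needs those two and every value in between. A patient who lacks the whole-period value for want of haemoglobin therefore also has at least one missing procedure value. Where missingness is heavy enough for the bias to matter, the whole-period measure will normally be main, and its patient-level imputation has no clustering to ignore. This stands, with one reservation: the SAP does not say whether missing values are counted by patient, by value or as a percentage of procedures.

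**The sign is not established.** The footnotes to Table 1 in section 7.2 require pre-procedure assessments only before surgery. One haemoglobin value may therefore end one procedure and start the next, entering the two with opposite signs and inducing negative correlation. Wound area and depth are already in the model, so shared wounds alone do not prove residual correlation. This stands too; body weight makes a positive sign plausible, not certain.

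**The size is assumption-driven.** Patients with one procedure have no clustering, and a whole run of dressing changes counts as one procedure. This is why the range starts at zero.

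**The Mann-Whitney branch is not covered.** It supplies no effect estimate and standard error of the kind pooled here, so the figures apply to the t-test branch only.

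None of this justifies the independence assumption, which is wrong under either sign.

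**Conclusion.** The point holds as a conditional, minor one. If residual blood loss is positively correlated within patients, the procedure-wise analysis reports a standard error about 0–10% too small for 1–3 procedures per patient and 10–40% missing. The shortfall is larger with more procedures and nil at zero correlation; negative correlation makes the error conservative. For scale, an SE ratio of 0.95 turns a nominal 5% test into 2[1−Φ(1.96×0.95)] = 6.3%, and a ratio of 0.90 into 7.8%.

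A reader might infer two stronger things that the document does not support. One is that the trial's confirmatory blood-loss test exceeds 5%. That needs positive correlation, appreciable missingness, the t-test branch, and the procedure-wise measure being main, and the last is unlikely. Because blood loss is last in the hierarchy, nothing would pass to another endpoint in any case. The other is that holding the residual SD fixed is a material cause. It is formally improper for Rubin's rules but worth under 1% of the standard error.

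**What to change.** In section 10.1.1.3, replace the procedure-level regression by a linear mixed model, fitted per arm with the same predictors plus a patient random intercept. In each of the 25 imputations, draw the fixed effects and the variance components, and predict missing values conditional on the patient's observed procedures. Drawing the residual variance comes with this and needs no separate justification.

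Using the mean of a patient's observed procedures as a predictor is not a substitute, because it is undefined when none is observed. A random intercept cannot represent negative correlation; its variance would then be estimated near zero, and the imputation would in effect return to the present model, whose error is conservative in that case.

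The cost is a few lines of code and usually slightly wider intervals. No data collection changes.

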7.2. Trial schedule

The healing and care of the burn wound may be divided into the three distinctive phases:

1. Eschar removal treatment phase (until complete eschar removal)
2. Wound management (until complete wound closure)
3. Scar modulation and maturation

These phases are common to the care of all wounds and are well defined in acute wounds such as burns.

In this study, these phases and their treatment strategy are equal for all arms, NexoBrid, SOC, and Gel Vehicle, following the ABA white paper recommendations [24].

The total duration of the study treatment and follow up period of each participating subject is expected to be 25 months: following the Eschar removal procedure, each subject will be followed up weekly (Weeks 1, 2, 3 and 4 etc.) until complete wound closure is achieved and 2 weeks later for wound closure confirmation, for each of the subject's TWs. Long-term follow-up visits will be performed at 1, 3, 6, 12, 18 and 24 months post last wound closure confirmation visit (for details see Table 1).

Table 1: Treatment flow chart - all arms³

If applicable
 * Weekly FU assessments will be performed every 7± 2 days from start of treatment until complete wound closure. Long-term FU will be performed 1,3,6,12,18 and 24 M after last wound closure confirmation.
 **First treatment session will include any procedure for eschar removal: the NexoBrid®/Gel Vehicle/Surgical or non-surgical procedure, as per randomization arm
 ** Procedure can be either surgical or non-surgical. A whole period of continuous dressing changes (from first coverage application to last coverage application) is considered as one non-surgical procedure, assessments should not be repeated for each dressing change; Pre procedures assessments refer only to surgical procedures. Post procedures assessments refer to any surgical procedures and for non-surgical procedure only if it is the last procedure

Parameter	Screening tests	Baseline within 1 h Pre First treatment session - All arms	Topical arms (NexoBrid or Gel Vehicle): (refer to first and second application). S=Soaking, R=Removal	SOC procedures** (including additional procedures in the topical arms)	Daily assessments	Management & Re-admissions ⁴ - surgical procedures assessment	Wound	HD or premature discontinuation visit	Weekly FU*	Long-Term FU (1, 3, 6,12,18 & 24 months)*
Inform Consent signing	X									
Medical history	X									
Burn History ⁵	X									
ConMeds & AEs	X	X	X	X	X	X	X	X	X	X

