10.3.3.3.5. Course of debridement procedure

For the multiple imputation outlined in Section 10.1.1.3 for each patient a categorical variable describing the course of the debridement process will be calculated. The different levels of the variable are defined as:

- Only non-surgical SOC debridement
- Non-surgical SOC debridement followed by surgical debridement
- Only surgical debridement
- Only NexoBrid debridement
- NexoBrid debridement followed by non-surgical SOC debridement followed by surgical debridement
- NexoBrid debridement follow by surgical debridement
- Only Gel Vehicle debridement
- Gel Vehicle debridement followed by non-surgical SOC debridement followed by surgical debridement
- Gel Vehicle debridement followed by surgical debridement

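### The procedure-level blood-loss imputation model is fitted to complete patients rather than complete procedures, so measured procedures can drop out of the fit

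*SAP*

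**What the plan says.** SAP Section 10.1.1.3 describes two multiple imputations for blood loss.

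- **Procedure-wise version.** The section expects gaps inside a patient: "Missing blood loss values for some eschar removal procedures may occur within a certain patient". The model is to be computed "on a procedure level treating all procedures as independent". Its covariates (area treated, the SPT, DPT and FT proportions, surgical or non-surgical type) are all defined for one procedure. Step 2 then gives the fitting set as "to the subset containing patients with complete data in those variables for both treatment groups separately". The fitted model is used to "calculate the predicted blood loss values for the procedures with missing blood loss using the covariate information".
- **Whole-period version.** One value per patient is modelled. The fitting set is described in the same words.

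Three other places bear on which values are missing.

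- Section 10.3.3.3.1 sums actual blood loss (ABL) over procedures "with the Hb measured immediately before each procedure and 4 hours after its completion".
- The legend of Table 1 (Section 7.2) says "A whole period of continuous dressing changes (from first coverage application to last coverage application) is considered as one non-surgical procedure", and also: "Post procedures assessments refer to any surgical procedures and for non-surgical procedure only if it is the last procedure".
- Section 10.3.3.3.5 lists "Non-surgical SOC debridement followed by surgical debridement" as one of the possible courses.

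**The concern.** If procedures are independent units, a gap in one procedure is no reason to discard another that was fully measured. As worded, the fitting set does exactly that: it selects on the patient, so one missing value removes all of that patient's rows. The patients whose gaps are to be filled then contribute nothing to the model that fills them, and patients with several procedures are the most likely to be lost.

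At stake are the regression coefficients and the residual SD from which the 25 imputations are drawn. They become less precise. They are also drawn from a selected group if patients with several procedures bleed differently from those with one.

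The schedule could make this systematic. A dressing period that ends in surgery has no post-procedure sample of its own in Table 1. If nothing else supplies its closing hemoglobin (Hb), its ABL is missing by design. Every patient with dressings before surgery would then leave the fit, even where the excision has both Hb values.

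**Working it through.** The SAP states no sample size, power or count for blood loss or its imputation, so there is no figure of its own to reproduce. The check is a comparison of texts followed by a conditional calculation.

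**1. Unit of the model against unit of the fitting set.** The model, its covariates and the values to be imputed are all at procedure level. The fitting set is at patient level. The phrase fits the whole-period model, where each patient is one row, but not the procedure-wise model.

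**2. Sporadic missingness (no schedule assumption).** Let each procedure's blood loss be missing independently with probability m. A measured procedure of a patient with k procedures stays in the fit only if the other k − 1 are also measured, so the share kept is (1 − m)^(k−1).

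- k = 2: 0.90, 0.80 and 0.70 for m = 10%, 20% and 30%.
- k = 3: 0.81, 0.64 and 0.49.

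The NexoBrid arm is an example. Section 9.2 anticipates excision in 0.24, so 75 × 0.24 = 18 patients. With one application and one excision each (assumed), a topical value missing in 10–30% removes about 2 to 5 of the 18 excisions from the fit. The values of m are assumptions.

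**3. Scheduled missingness (if the dressing period has no usable closing Hb).**

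- SOC arm: 75 (Section 9.3.1). Anticipated SOC excision rate: 0.60 (Section 9.2).
- Expected excised SOC patients: 75 × 0.60 = 45, with one measured excision each (assumed).
- f = share of these with dressings first. The SAP does not give it; assumed range 25% to 75%.
- Excisions kept = 45 × (1 − f). SE ratio for a mean over excisions = √(45 / kept).

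| f | Kept, patient rule | Kept, procedure rule | SE ratio |
|---|---|---|---|
| 25% | 33.75 (about 34) | 45 | 1.15 |
| 50% | 22.5 (22–23) | 45 | 1.41 |
| 75% | 11.25 (about 11) | 45 | 2.0 |

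**4. Which blood-loss version becomes the main analysis.** Sections 7.3.2.2, 10.3.3.3.1 and 11.1.3.3 give that role to the version with fewer missing values. The whole-period version needs the Hb before the first procedure and the Hb 4 hours after the last. The procedure-wise sum needs those two and all values in between. A patient with every procedure-wise Hb therefore also has both whole-period Hb values. Counted per patient, the whole-period version cannot have more patients with missing Hb, and any scheduled gap in between adds to the procedure-wise count only.

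**The case against.** Four points can be made against the concern.

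- **Loose wording.** The fitting phrase is shared with the whole-period block, and the transfer also runs the other way: the patient-level model speaks of predicting for procedures. The author may simply have meant complete rows, which is what a regression routine would use by default. This is plausible and may describe the intent. The text still does not say so, and Section 6.4 has a second statistician implement the secondary endpoints independently. Two programmers could fit different sets and obtain different imputations from the same seeds.
- **Loss of every dressings-then-surgery patient.** A reader might infer this from Table 1 as a fact. The SAP does not settle it. The amendment summary in Section 13.5.1 (version 9 to 11, line 26) explains that a non-surgical procedure that is not the last is followed by surgery, with assessments taken before that surgery. The pre-surgery Hb might therefore close the dressing period. Section 10.3.4.4 states a substitution rule of this kind for vital signs, but the SAP gives none for Hb, so the point stays open.
- **Harm to the fourth confirmatory test.** A reader might infer this too, since blood loss is fourth in the hierarchy of Section 11.1.8. Step 4 of the working speaks against it: the more the schedule creates gaps, the more clearly the procedure-wise analysis becomes supportive, leaving the test to the patient-level model, where the wording is appropriate.
- **Measured values are not lost.** Measured excisions still enter the patient's summed ABL; they leave only the imputation fit. This is correct.

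**Conclusion.** The concern holds as a defect in how the procedure-level fitting set is specified. Taken literally, the wording discards measured procedures from the imputation fit, with no gain to set against the loss of precision.

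The size depends on figures the SAP does not give. With sporadic gaps alone and two procedures per patient, 10–30% of measured procedures in such patients leave the fit at 10–30% missingness. If dressing periods before surgery also have no usable closing Hb, about 34, 22–23 or 11 of 45 SOC excisions remain for assumed shares of 25%, 50% or 75%. The SE of a surgical mean is then 1.15, 1.41 or 2.0 times as large. Bias arises only if patients with mixed courses bleed differently, and the SAP has no figure on that.

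The effect falls mainly on the procedure-wise analysis, which is likely to be supportive. An effect on the confirmatory blood-loss test is not established, and neither is the automatic loss of all dressings-then-surgery patients.

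**What to change.** In step 2 of the procedure-level imputation in Section 10.1.1.3, define the fitting set as all procedures with complete data in the model variables, whether or not other procedures of the same patient are missing. Keep the patient as the unit only in the whole-period model.

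In Section 10.3.3.3.1, state which Hb value closes a dressing period that is followed by surgery, or state that its ABL is to be treated as missing. This second change is needed because the first does not supply the missing dressing periods. If they remain missing, they are imputed from dressing periods that ended the debridement, and excisions inform them only through the shared slopes and residual SD.

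The cost is one changed phrase and one added sentence, with no new data or visits.
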